7.3 SAS Codes for Chi-Square Test

The confidence intervals and the p-value for the chi-square test can be produced by the following SAS code.

```
proc freq data=;
  tables xx/binomial(p=) alpha=;
  run;
```

For example, the worst case scenario in the PG testing of the primary safety hypotheses is used for the exercise. A dummy frequency table is coded as below.

```
%let total=50; %let yes=49; %let no=&total.-&yes.;

data dsn1;
  yn=1; wgt=&yes.; output;
  yn=0; wgt=&no.; output;
run;
```

A list of SAS codes for Binomial and Chi-Square method is used for PG=88% and 95% confidence limits.

```
proc freq data=dsn1 order=data;
  tables yn/ binomial(p=0.88) alpha=.05;
  weight wgt;
run;
```

The SAS output for the worst case scenario is presented below.

Binomial Proportion	
yn = 1	
Proportion	0.9800
ASE	0.0198
95% Lower Conf Limit	0.9412
95% Upper Conf Limit	1.0000
Exact Conf Limits	
95% Lower Conf Limit	0.8935
95% Upper Conf Limit	0.9995
Test of H0: Proportion = 0.88	
ASE under H0	0.0460
Z	2.1760
One-sided Pr > Z	0.0148
Two-sided Pr > Z	0.0296
Sample Size = 50	

7.4 SAS Codes for Paired T-Test

The confidence intervals and paired t-test p-value can be produced by the following SAS code.

```
proc ttest data=;
  paired post*prior;
run;
```

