3.2.1 Definition of Acute Reduction

The acute reduction of %DS is defined to compare the post atherectomy but prior to any adjunctive therapy to its baseline diameter stenosis.

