3.2.2 Effectiveness Hypotheses

The primary effectiveness hypothesis to be tested is that the acute reduction of %DS in subjects treated with Jetstream System exceeds 40%* within subject at a one-sided significance level of 2.5%.

The null hypothesis (H_0) states that there is no treatment effect before and after subjects treated with Jetstream System as opposed to the alternative hypothesis (H_1) which states that there is a treatment effect. The hypotheses inequalities are shown below:

$$H_0: \Delta t \leq 0 \text{ (not met)}$$

$$H_1: \Delta t > 0 \text{ (met)}$$

where Δt is the averaged difference in acute reduction of %DS before and after the subjects treated with Jetstream System and the within-subject treatment effect is 40% with standard deviation of 18% derived by the Pathway PVD study, Jetstream Calcium study and JET Registry.

*The expected mean acute reduction (i.e. %DSbefore Jetstream – %DSafter Jetstream) was 40%; the primary effectiveness hypothesis is to demonstrate there is a significant acute reduction (>0).

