3.2.5 Worst Case Assessment for Effectiveness

The mean and standard deviation of the reductions are based on each subject's change in %DS before and after atherectomy. If the standard deviation of 18% is observed, the acute reduction of %DS will be at least 6% to claim a success. Other scenarios are shown below.

Standard Deviation in Reduction (%DS)	Minimal Diff in Reduction (%DS)
8-10	3
11-14	4
15-17	5
18-21	6
22-24	7
25-28	8
29-31	9
32-35	10

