3.3.2 Success Criteria for the effectiveness Endpoint

Jetstream System will be concluded as meeting endpoint for device effectiveness if the one-sided lower 97.5% confidence bound on the difference between before and after atherectomy in %DS within subject is greater than zero.

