5.15 Analyses Software

All statistical analyses will be performed and validated by the independent CRO (e.g. IQVIA in Bangalore) using the Statistical Analysis Software (SAS), version 9.2 or later (Copyright © 2002-2010 by SAS Institute Inc., Cary, North Carolina 27513, USA. All rights reserved). BSC will review statistical reports.

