6 VALIDATION

All clinical data reports generated per this plan will be validated per 90702587, Global WI: Clinical Data Reporting Validation. Statistical analyses and validation will be done by an independent CRO.

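### Does the sample code in SAP 7.4 test the primary effectiveness endpoint in the wrong direction?

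*SAP*

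**What the plan says.** The direction of the effect is set in the body of the SAP. Section 3.2.2 states: "The expected mean acute reduction (i.e. %DSbefore Jetstream – %DSafter Jetstream) was 40" (percent). It pairs this with a null of no reduction and an alternative of a mean difference above zero. Section 3.3.2 rests success on a one-sided lower bound at the 97.5% level, that is, a "confidence bound on the difference between before and after atherectomy in %DS within subject is greater than zero". Section 3.2.5 lists the smallest observed reductions that would pass, all as positive numbers: "If the standard deviation of 18% is observed, the acute reduction of %DS will be at least 6% to claim a success".

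Section 7.4 offers code that can be used to obtain the interval and p-value. The data set name is left blank, the variables line is "paired post*prior", and neither variable is defined. No worked output follows, whereas section 7.3 gives a dummy data set and full output for the primary safety test.

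On execution, section 5.15 has the analyses "performed and validated by the independent CRO", with the sponsor reviewing the statistical reports. Section 6 adds: "All clinical data reports generated per this plan will be validated per 90702587", which is a named work instruction.

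**The concern.** The template in 7.4 is the only code the SAP gives for the primary effectiveness test. If the software forms the first variable minus the second, an effective device produces a negative mean difference and a negative lower limit. Someone who took that printed lower limit as the bound in 3.3.2 would record the endpoint as not met, however large the fall in stenosis. An upper-tailed p-value from the same output would also point the wrong way.

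The undefined names add to the unease. Section 3.2.1 says the endpoint is to "compare the post atherectomy but prior to any adjunctive therapy to its baseline diameter stenosis", so the word prior is attached there to the post-atherectomy reading and not to baseline. A literal-minded programmer could ask which reading each name stands for. Because study success needs both primary endpoints, a sign error carried through to the decision would matter.

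**Working it through.** **Inputs.** Mean reduction 40 and SD 18 (SAP 3.2.3); 50 evaluable subjects and a paired t-test (SAP 3.2.4); primary cohort of 60 (SAP 3.1.3); one-sided alpha 2.5% (SAP 3.2.3); threshold case of 6 points at SD 18 (SAP 3.2.5).

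**Assumptions not in the documents.** (1) In SAS, `paired a*b` analyses a minus b. (2) Post is %DS after atherectomy and prior is baseline %DS.

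**Step 1: reproduce the SAP's own figure.** The smallest passing mean is t(0.975, n-1) × SD/√n. With n = 50, t(0.975, 49) = 2.0096, so 2.0096 × 18/√50 = 2.0096 × 2.5456 = 5.12, which rounds up to the stated 6. The other seven rows of the table in 3.2.5 reproduce in the same way. A normal quantile would give 4.99, rounding up to 5, so the table is t-based. The SAP's own threshold arithmetic therefore uses a positive reduction tested against zero, as 3.2.2 and 3.3.2 say.

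**Step 2: compute the interval in both orders** (mean ± half-width; the half-width is 5.116 at n = 50, and 2.0010 × 18/√60 = 4.650 at n = 60).

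| Case | Before minus after (SAP 3.2.2) | After minus before (SAP 7.4 as printed) |
|---|---|---|
| Mean 40, n = 50 | 34.88 to 45.12 | -45.12 to -34.88 |
| Mean 40, n = 60 | 35.35 to 44.65 | -44.65 to -35.35 |
| Mean 6, n = 50 | 0.88 to 11.12 | -11.12 to -0.88 |

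**Step 3: compare the test results in the threshold case.** t = 6/2.5456 = 2.357 in one order and -2.357 in the other. The two-sided p is 0.0225 both ways. The upper-tail p is 0.0112 for before minus after and 1 - 0.0112 = 0.9888 for after minus before.

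**Step 4: relate the two decision rules.** Let L be the lower limit for before minus after, and U the upper limit for after minus before. Then U = -L, so L > 0 holds exactly when U < 0. In the threshold case L = 0.88 and U = -0.88. No data set passes one rule and fails the other. The order of the variables decides only which printed limit carries the decision.

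**The case for a change.** The best case for amending 7.4 is that the correction is almost free and the SAP text is the handover to an outside programming group. Section 7.3 shows a worked safety example with lower limits and an upper-tailed p-value. Someone who carried that habit into 7.4 would look at the wrong limit or the wrong tail, and 7.4 has no sample output to alert them. Two undefined names, one echoing a word used differently in 3.2.1, make the template looser than it needs to be.

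Part of this stands. Under the two assumptions the order does disagree with 3.2.2, and the names are undefined. The step from there to a wrong conclusion does not stand:

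- The code is a syntax template that cannot run as printed, since its data set is blank. Whoever completes it must supply the data set and map the variables, and takes the endpoint definition from section 3.
- Section 3.2 already fixes the timing of the second reading, and section 4.2 already requires core-laboratory data for the effectiveness endpoint. In a two-variable before-and-after test, post and prior have one natural reading.
- The order in the code follows the wording of 3.2.1, which compares the later reading with baseline. The disagreement is with the sign convention in 3.2.2, not with every definition in the SAP.
- The error would announce itself. At planning values the output would show a mean of -40 for a quantity expected to be +40.

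**Conclusion.** This is a clerical slip in illustrative code. The printed order gives the negative of the defined reduction, provided that the software subtracts the second variable from the first and that the names have their natural meaning. Sections 3.2.2 and 3.3.2 state the hypothesis and the success rule correctly, and they govern. The limits swap places and change sign, by the same 5.12-point half-width at n = 50; the absolute t statistic, two-sided p-value, power and sample size are untouched. A correctly read result is identical in either order, down to the threshold case with its bound of 0.88. A false not-met finding would need 3.3.2 to be misapplied and the mistake to survive validation and sponsor review. An analyst will either reverse the two names or read the upper limit against zero, and both give the planned decision. An amendment would gain nothing of substance.
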